Approximately 740 patients will be screened in order to randomize/enroll approximately 555 patients, such that approximately 444 evaluable patients complete the 24-week of double-blind period of the trial.

Key Eligibility Criteria:

A full listing of eligibility criteria can be found in [Section 5](#). Patients are eligible to be included in the trial only if all criteria are met.

Key Inclusion Criteria

- Males or Females between the ages of 18 and 80 years of age, inclusive
- Diagnosis of familial or sporadic ALS (defined as meeting the laboratory-supported probable, probable, or definite criteria for ALS according to the World Federation of Neurology El Escorial criteria published in 2000 [[Brooks 2000](#)]). Patients who meet the possible criteria are eligible if they have lower motor neuron findings; those who have purely upper motor neuron findings are ineligible.
- First symptom of ALS \leq 24 months prior to screening. The qualifying first symptoms of ALS are limited to manifestations of weakness in extremity, bulbar, or respiratory muscles. Cramps, fasciculations, or fatigue should not be taken in isolation as a first symptom of ALS.
- ALSFRS-R total score \leq 44 at screening. Patients with a total score of 45 or higher may be rescreened 60 ± 7 days following the original screening date and be deemed eligible if their ALSFRS-R total score is \leq 44 or if their score is 2 or more points less than at initial screening. Such patients must continue to meet all other inclusion/exclusion criteria at the time of rescreening.
- Upright FVC \geq 65.0% of predicted for age, height, sex and ethnicity at screening according to Global Lung Initiative equation
- Able to perform reproducible pulmonary function tests defined as being able to perform FVC at screening with variability of the 2 highest raw values of less than 10% with a maximum of 5 trials permitted. Screening FVC results must be reviewed and approved by the central review process prior to randomization.
- Must be either on riluzole for \geq 30 days prior to screening or have not taken it for at least 30 days prior to screening

- Must have completed at least 2 cycles of edaravone at the time of screening or have not received it for at least 30 days prior to screening
- Able to swallow whole tablets at the time of screening

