### **8.4. Subgroup Analyses**

#### **8.4.1. Subgroups for Explanation of Potential Heterogeneous Treatment Effect**

Subgroup analyses with relatively moderate sample size will be performed to examine the consistency of the observed treatment effect and to gain insight into the effectiveness of reldesemtiv in subpopulations. Analyses of the primary endpoint and the first secondary endpoint will be conducted for the following subgroups:

- Sex (male, female)
- Age group (< median, ≥ median)
- Race (white, non-white)
- BMI at baseline (< 25 kg/m^2, ≥ 25 kg/m^2)
- Riluzole and edaravone use status at baseline (use riluzole, use edaravone, use neither).
- Percent predicted FVC at baseline (< median, ≥ median)
- ALSFRS-R total score at baseline (< median, ≥ median)
- Geographic region (North America, Europe, Australia)
- Anatomic site of disease onset (upper limb, lower limb, limb, bulbar, cognitive, respiratory)
- Time since ALS symptom onset (< 1.5 years, ≥ 1.5 years)
- Pre-study rate of disease progression (1st tertile, 2nd tertile, and 3rd tertile)
- MiToS at baseline (Stage 0, Stage 1, Stage 2, Stage 3 and Stage 4)

For the primary endpoint (ALSFRS-R total score change from baseline to Week 24):

- The MMRM with the subgrouping factors being added to the primary analysis model (see [Section 8.6.1](#)) will be used to produce treatment comparisons at each visit for each subgroup. The subgrouping factors include: the “subgroup” listed above as well as “subgroup-by-treatment”, “subgroup-by-visit”, and “subgroup-by-treatment-by-visit” interactions. If the MMRM fails to converge, an ANCOVA model with change from baseline to Week 24 as response variable and model terms listed as follows will be used to perform the analysis: treatment, baseline riluzole use, baseline edaravone use, baseline ALSFRS-R total score, covariates identified before the database lock (see [Section 8.6.1](#)), subgroup and subgroup-by-treatment interaction.

For the first secondary endpoint (combined assessment of change in ALSFRS-R total score, time to dependence on assisted ventilation (either invasive or non-invasive), and survival time up to Week 24):

- The joint rank test subsequent to the MAR imputation of missing ALSFRS-R total scores at Week 24 (see [Section 8.7.1](#)) will be applied for all subgroups.

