## 8.6. Analysis of the Primary Efficacy Endpoint

### 8.6.1. Primary Efficacy Analysis

The primary efficacy endpoint of the trial is the change from baseline to Week 24 in ALSFRS-R total score. The estimand of the primary efficacy endpoint is the difference in the mean changes from baseline to Week 24 in ALSFRS-R total score between patients randomized to placebo and those randomized to reldesemtiv in the FAS.

The analysis for the primary efficacy endpoint will be conducted using a mixed model for repeated measures (MMRM) based on a restricted maximum likelihood method (SAS® PROC MIXED default). The model terms will include treatment group, baseline ALSFRS-R total score, visit, riluzole use at baseline, edaravone use at baseline as well as baseline-by-visit and treatment group-by-visit interactions. In addition, other baseline covariates identified by stepwise selection in a regression model will also be included in the model if they are key predictor variables for the change from baseline to Week 24 in ALSFRS-R total score. The regression model used to identify baseline covariates will include change from baseline to Week 24 in ALSFRS-R total score as response variable and pre-study disease progression rate, age and baseline percent predicted FVC as model terms. The stepwise selection process with significance at 0.25 level for a variable to be entered to the model and with significance at 0.1 level for a variable to remain in the model will be used. The best-fit model according to AIC will be selected. The evaluation will be performed based on the blinded data before the database lock. An unstructured variance-covariance matrix will be used for the model. Observed data collected up to Week 24 in the FAS will be included in the model.

Prior to applying the MMRM, multiple imputation with fifty invocations under the MAR paradigm will be performed to impute missing data (see [Section 8.6.1.1](#) for imputation method).

Least squares mean (LSM), LSM difference and the corresponding standard error, 95% CI and p-value will be presented. The components used to derive main estimator of the primary analysis are shown in [Table 4](#).

Sensitivity analyses will be conducted to support the robustness of conclusions based on the primary analysis results. See [Section 8.6.2](#) for sensitivity analyses.

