### **8.6.1.1. Imputation of the Missing Data for the Primary Efficacy Analysis**

The extent of missing data and the pattern of missing data reasons will be tabulated. Missing ALSFRS-R total score will be imputed for the primary efficacy analysis described in [Section 8.6.1](#). For each randomized treatment group, the missing data will be filled sequentially starting at the earliest time point and progressing until the last time point based on a multivariate joint normal imputation model ([Schafer 1997](#)). The imputation model will include the following terms: ALSFRS-R total score at previous visits including baseline (in reldesemtiv or placebo group), riluzole use and/or edaravone use at baseline, and other covariates selected using stepwise regression for the primary analysis (see [Section 8.6.1](#)) such as pre-study disease progression rate, age and/or baseline percent predicted FVC. Fifty set of complete data will be generated for analysis to produce 50 sets of estimates. Rubin's imputation rules ([Rubin 1987](#)) will be used to combine the LSM estimates of the treatment difference, 95% confidence interval and p-value. The example SAS code can be found in [Section 12.5](#).

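### The imputation model behind the SAP 8.4 subgroup analyses omits most subgroup factors, so subgroup-by-treatment differences are modestly shrunk

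*SAP*

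**What the plan says.** SAP 8.4.1 lists twelve subgroup factors. For the primary endpoint it uses the MMRM "with the subgrouping factors being added to the primary analysis model": subgroup, subgroup-by-treatment, subgroup-by-visit and the three-way term. It cross-refers to SAP 8.6.1, where the order of work is: "Prior to applying the MMRM, multiple imputation with fifty invocations under the MAR paradigm will be performed to impute missing data". An ANCOVA is the fallback if the MMRM does not converge. For the first secondary endpoint the subgroup method is "The joint rank test subsequent to the MAR imputation of missing ALSFRS-R total scores at Week 24", and SAP 8.7.1.1 sends that imputation to SAP 8.6.1.1.

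SAP 8.6.1.1 imputes by arm: "For each randomized treatment group, the missing data will be filled sequentially starting at the earliest time point". The terms are "ALSFRS-R total score at previous visits including baseline (in reldesemtiv or placebo group), riluzole use and/or edaravone use at baseline", plus covariates kept by the stepwise selection, "such as pre-study disease progression rate, age and/or baseline percent predicted FVC". No subgroup-specific imputation is described anywhere.

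SAP 8.4.2 puts the subgroup covariates and their interactions with treatment into the primary MMRM. If the primary or first secondary result is significant and the global interaction test has p below 0.05, the selected covariates are labelled treatment effect modifiers.

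**The concern.** The analysis model estimates an interaction that the imputation model does not represent. Given the earlier scores, a patient who drops out is assumed to follow the arm-wide course whatever the subgroup. The imputed part of the data therefore understates how treatment effects differ between subgroups.

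SAP 8.4.1 exists to check whether the effect is consistent, and this imputation leans towards consistency. A shrunken interaction also bears on the labelling rule in SAP 8.4.2. The question is live in this programme: Protocol 4.2 reports that the Phase 2 effect was more evident in faster progressors and in patients with symptoms for 24 months or less and a baseline score of 44 or less. Time since onset never enters the imputation model, and progression rate enters only if it is selected.

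**Working it through.** **1. The plan's own figure and the missing-data rate.** Inputs from SAP 4.3.1: difference 1.8, SD 5.5, two-sided alpha 0.05, power 90%, 2:1 allocation.

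Placebo n = (1.960 + 1.282)² × 5.5² × (1 + 1/2) / 1.8² ≈ 10.51 × 30.25 × 1.5 / 3.24 ≈ 147.2, so 148 placebo and 296 reldesemtiv, 444 in all. Then 444 / 0.80 = 555, which reproduces the plan. No dropout rate is stated. The 20% follows from the Synopsis, which plans 555 randomized "such that approximately 444 evaluable patients complete the 24-week of double-blind period of the trial": 1 − 444/555 = 0.20.

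**2. Which factors the imputation model contains.**

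- In the model by text (2): riluzole/edaravone use and baseline ALSFRS-R.
- Only if selected (3): age, baseline percent predicted FVC, pre-study progression rate.
- Never (7): sex, race, BMI, region, site of onset, time since onset, MiToS stage.

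The sample code in SAP 12.5 is narrower still: riluzole, edaravone and post-baseline scores only.

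**3. Size of the shrinkage.** If a fraction m of Week 24 scores is missing, and the imputed scores carry a share f of the true interaction, the share retained is R = (1 − m) + m × f. A patient with no post-baseline score has f close to 0, so at m = 0.20 the floor is R = 0.80. How far f rises above 0 depends on how much of the subgroup difference the patient's earlier scores already show.

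This was simulated with 600,000 patients at 2:1, sequential regression imputation by arm on all earlier scores including baseline, then a Week 24 model with treatment, subgroup, their interaction and baseline. Assumptions not in the documents: baseline SD 5; linear decline with random slopes scaled to a change SD of 5.5; two equal subgroups with effects 0.6 and 3.0 (mean 1.8, interaction 2.4); dropout unrelated to outcome. Share of the interaction retained at 20% missing:

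| Last score before dropout | Visit residual SD 1.5 | Visit residual SD 2.5 |
|---|---|---|
| Week 20 | 98% | 95% |
| Week 12 | 95% | 90% |
| Spread evenly, Weeks 4 to 20 | 93% | 89% |
| Week 4 | 84% | 82% |
| Baseline only | 80% | 80% |

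With even dropout, f = (0.93 − 0.80)/0.20 = 0.65 or (0.89 − 0.80)/0.20 = 0.45. So the earlier scores recover roughly half of what would otherwise be lost. At residual SD 1.5, 10% missing retains 96% (even) or 92% (after Week 4), and 30% missing retains 88% or 76%. With the subgroup factor in the imputation model, 99 to 101% is retained in every setting.

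**4. Against sampling error.** On an interaction of 2.4 the loss is 0.07 × 2.4 = 0.17 to 0.11 × 2.4 = 0.26 points. With 444 completers in two equal subgroups the standard error of the interaction is about 2 × 5.5 × √(1/296 + 1/148) = 1.11, so the bias is about 0.15 to 0.24 standard errors.

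**5. Power, precision and the joint rank test.** In trial-level simulation of the even-dropout case, power to detect the interaction without versus with the factor was 61% versus 64% (residual SD 1.5) and 56% versus 62% (residual SD 2.5). Root mean squared error was 1.00 without the factor and 1.06 to 1.10 with it. The between-subgroup difference in Mann-Whitney probability shrank by a similar 7 to 11%.

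**The case against.** Four points can be made for the plan.

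- A reader might infer that missing scores are filled with the arm average. They are not. SAP 8.6.1.1 conditions on the patient's own earlier scores, which carry much of any subgroup divergence. Filling from the arm average would lose about 20%, and that picture fits only patients with no post-baseline score.
- A reader might infer that every subgroup analysis is affected. Two factors are in the model by text and three may be. Because imputation is by arm, the interactions of those factors with treatment are largely allowed for. MiToS stage is derived from ALSFRS-R items, so the baseline total carries part of it.
- Reuse of the imputations for the subgroup MMRM is not stated. SAP 8.6.1 also says that observed data up to Week 24 enter the model, and the ANCOVA fallback names no imputation. Reuse is the natural reading of the cross-reference, but it remains a reading. For the joint rank test it is explicit.
- The practical loss is small. In a separate simulation of 400 trials at 20% missing, coverage of the 95% interval was 96% with or without the factor for an interaction of 3.6. With no true interaction there was no bias, and rejection was 2.5% without versus 4.5% with the factor. Overall error is no larger under the plan, because the bias is offset by lower variance.

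All four stand as limits on the point. They do not remove it: the shrinkage has a known direction, it affects an analysis the SAP explicitly bases on imputed data, and it works against detecting the heterogeneity that SAP 8.4 is meant to look for.

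**Conclusion.** The point holds in a limited form. For the seven factors that can never enter SAP 8.6.1.1, and for age, FVC and progression rate if they are not selected, subgroup-by-treatment differences are understated. The size is about 7 to 11% at 20% missing with dropout spread over visits, 2 to 5% if dropout follows Week 20, and 16 to 18% if it all follows Week 4. The dropout pattern, the residual SD and dropout unrelated to outcome are assumptions. The direction was the same in every setting with a true interaction.

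A reader might go further and doubt the trial's main conclusion. The documents give no ground for that: these analyses examine consistency and are supportive, they lie outside the SAP 8.5 sequence, and the primary estimate, its error rate and its power do not depend on them. The change is worth making because it is cheap, not because a confirmatory decision is at risk.

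**What to change.** State in SAP 8.4.1 and 8.4.2 which data each subgroup analysis uses, then:

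- **Primary endpoint.** Fit the 8.4.1 subgroup MMRM and the 8.4.2 interaction model to observed data without imputation, as Sensitivity Estimator 1 does. Alternatively, add the tested subgroup factor to the by-arm imputation model. The first route is simpler for 8.4.2, where many covariates are considered together and a matching imputation model would be large.
- **Joint rank test.** Add the subgroup factor to the by-arm imputation model. Pool sparse levels, notably the six site-of-onset and five MiToS categories, since the placebo arm has only about 555/3 = 185 patients.
- **Sample code.** Bring SAP 12.5 into line with SAP 8.6.1.1, as it omits baseline ALSFRS-R and the selected covariates.

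The cost is SAP wording, one re-run of the imputation per factor where that route is taken, and slightly larger variance of the subgroup estimates.

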#### **8.4.2. Subgroups Supportive Analyses for the Primary Analyses of Primary Endpoint and First Secondary Endpoint**

To explain potential heterogeneity and identify treatment effect modifiers from the baseline characteristics, covariates used to define pre-specified subgroups and these covariates by treatment interaction terms will be included in the primary analysis MMRM model as supportive analysis. Covariates measured as continuous will be introduced to the model as continuous variable. Global test of covariates by treatment interactions will be performed. Stepwise model selection method will be used based on the default stay or entry level of 0.1 to evaluate

significant baseline covariates. The p-value of global test of covariates by treatment group interaction terms as well as the p-values in an ascending order and treatment difference evaluating individual covariates by treatment interactions will be provided from the final multivariate interaction model.

If the primary analysis for the primary endpoint or the first secondary endpoint is significant and the global test of covariates by treatment interactions are having 2-sided p-value less than 0.05, the selected baseline covariate(s) will be considered as treatment effect modifier(s). The corresponding pre-specified subgroup analyses will be considered to explain the potential heterogeneous treatment effect.

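### SAP 8.4.2, as most naturally read, tests treatment interactions globally after stepwise selection at 0.1, so with no heterogeneity the 5% test rejects in about half of trials

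*SAP*

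**What the plan says.** SAP 8.4.1 lists twelve baseline factors: sex, age, race, BMI, riluzole/edaravone use, percent predicted FVC, ALSFRS-R total score, region, site of onset, time since symptom onset, pre-study progression rate and MiToS stage. SAP 8.4.2 adds these factors and their treatment interactions to the primary MMRM, in order "To explain potential heterogeneity and identify treatment effect modifiers from the baseline characteristics, covariates used to define pre-specified subgroups and these covariates by treatment" interactions. Continuous factors stay continuous: "Covariates measured as continuous will be introduced to the model as continuous variable".

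The section then does four things in this order.

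1. It says that a global test of the interactions will be performed.
2. It introduces selection: "Stepwise model selection method will be used based on the default stay or entry level of 0.1".
3. It says where the reported results come from. "The p-value of global test of covariates by treatment group interaction terms", together with the ordered individual interaction p-values, "will be provided from the final multivariate interaction model".
4. It sets the decision rule, which operates only if the primary or first secondary endpoint is significant: "interactions are having 2-sided p-value less than 0.05, the selected baseline covariate(s) will be considered as treatment effect modifier(s". The matching subgroup analyses are then to be considered as an explanation of heterogeneity.

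The section calls the analysis supportive. It contains no correction for selection.

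**The concern.** The only global p-value whose source is stated comes from the final model, which is the model left after selection. The rule then acts on the selected covariates. If stepwise selection acts on the interaction terms, every term in that joint test is there because its own p-value was below 0.1. The reference distribution of an ordinary joint test ignores this, so 0.05 is no longer the error rate.

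The rule decides whether the report names effect modifiers and uses subgroup results to explain them. It does so only in a trial with a significant result, where such statements will be read most closely.

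**Working it through.** **The plan's own figure.** SAP 4.3.1 gives a difference of 1.8, SD 5.5, two-sided alpha 0.05, power 90% and 2:1 allocation. Placebo n = (1 + 1/2) × 5.5² × (1.960 + 1.282)² / 1.8² = 147.2, rounded up to 148. The total is 3 × 148 = 444, and 444 / 0.80 = 555. Power at 148:296 is 0.902. This reproduces the plan's 444 evaluable and 555 randomized.

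**Bounds by hand.** Take 12 independent interactions of 1 df each and no true heterogeneity.

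- P(at least one retained at 0.1) = 1 − 0.9^12 = 0.718.
- P(at least one below 0.05) = 1 − 0.95^12 = 0.460. This is a lower bound on rejection. If one retained term has chi-square above 3.84 and each other retained term exceeds 2.71, the sum passes the joint critical value: 6.55 against 5.99 on 2 df, 9.25 against 7.81 on 3 df, and so on.
- The joint test cannot reject if nothing is retained, or if the only retained term lies between 0.05 and 0.1. The latter has probability 12 × 0.05 × 0.9^11 = 0.188. Rejection is therefore at most 0.718 − 0.188 = 0.529.

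So the null rejection rate lies between 46.0% and 52.9%.

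**Monte Carlo, independent chi-squares (200,000 runs): keep terms with p < 0.1, test them jointly at 0.05.**

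| Candidates | Test after selection | Full-set test |
|---|---|---|
| 12 × 1 df | 52% | 5% |
| 12 factors, 21 df | 52% | 5% |
| 10 × 1 df | 45% | 5% |
| 8 × 1 df | 37% | 5% |
| 6 × 1 df | 29% | 5% |

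The 21 df follow the SAP 8.4.1 list with age, BMI, FVC, ALSFRS-R, time since onset and progression rate continuous: 8 factors at 1 df, 2 at 2 df (riluzole/edaravone, region), onset site at 5 and MiToS at 4.

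**Stepwise simulation (1,500 trials per row).** True effect 1.8 points, no interaction, 2:1 allocation, 12 factors of mixed df, main effects kept in, entry and stay at 0.1.

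| Setting | Any term retained | Rejects after selection | Full-set test rejects |
|---|---|---|---|
| n = 555, uncorrelated | 72.7% | 52.6% | 4.5% |
| n = 555, correlated | 71.6% | 51.9% | 4.7% |
| n = 444, correlated | 67.0% | 49.5% | 4.8% |
| n = 555, correlated, backward elimination | 70.8% | 51.9% | 5.2% |

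This uses a Week 24 ANCOVA in place of the MMRM. Category proportions, prognostic effects and correlations are assumptions, and some sparse categories were merged.

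**Adding the significance condition.** With power 0.902 and independence of the two events, the joint rate is 0.902 × 0.495 = 0.446 to 0.902 × 0.526 = 0.474, or about 45 to 47%.

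**Other readings of 8.4.2.** If stepwise selection acts only on covariate main effects, a 3,000-trial simulation gave 5.3%. If the full-model test decides, it gave 5.5%.

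**The case against.** The strongest objection is that the text is open. A global test is mentioned directly after all covariates and interactions enter the model, before stepwise selection appears. Selection is then said to evaluate significant baseline covariates, not interactions. If the full-model test decides, or if only main effects are selected, the error rate is about 5% and there is no problem of size. This stands as far as it goes: the inflation belongs to one reading. But that reading fits the words best, because the reported global p-value is tied to the final interaction model and the covariates declared modifiers are the selected ones. A plan that permits both a 5% and a 50% error rate needs the edit in either case.

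A reader might infer more than the documents support:

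- *That the procedure usually labels noise.* It operates only after a significant primary or first secondary endpoint. At the planned effect the joint rate is just under half; if the drug has no effect, the condition is rarely met.
- *That confirmatory error is inflated.* The analysis is labelled supportive and lies outside the closed testing procedure of SAP 8.5.
- *That product labelling is at stake.* Neither document links 8.4.2 to labelling.
- *That the missing visit term contributes to the 50%.* SAP 8.4.2 names covariate-by-treatment terms without visit, so read literally it tests a modification held constant over visits, whereas 8.4.1 includes a subgroup-by-treatment-by-visit term. That is a separate, unquantified point, and 8.4.1 already gives visit-specific subgroup estimates.

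**Conclusion.** The rule is wrong as written on its most natural reading and should be changed. With no heterogeneity, the post-selection global test rejects in about 50% of trials with 12 candidates and about 29% with 6 effective candidates, against a nominal 5%.

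The size rests on stepwise selection acting on the interaction terms, on roughly 12 effective candidates, and on a Week 24 ANCOVA standing in for the imputed MMRM. Correlation, sample size between 444 and 555, and the df layout change it little; fewer effective candidates lower it. The 45 to 47% joint figure also assumes the planned 1.8-point effect and independence from the primary result. A significant first secondary endpoint alone could also open the rule, which would move the figure towards the unconditional 50%.

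The consequence is limited to false modifier declarations and the subgroup explanations drawn from them.

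**What to change.** In SAP 8.4.2:

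1. State that the deciding global test is run once, on the full pre-specified set of covariate-by-treatment interactions, before any selection.
2. Direct it at the Week 24 effect, for example with the Week 24 ANCOVA that 8.4.1 already names as its fallback, and pool it over the 50 imputed datasets.
3. Remove the p < 0.05 decision rule from the final selected model.
4. Say which terms stepwise selection acts on, and report the selected covariates and their p-values as exploratory.

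Visit-specific interactions for all factors in the unstructured MMRM are not advisable. With 21 df and six post-baseline visits that is 21 × 6 = 126 interaction parameters, and 8.4.1 already plans for non-convergence with one subgroup factor.

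**Cost.** A few sentences, 50 model fits and a multivariate pooling rule for the joint test. The full-set test also has low power for a single modifier: in a 21-df simulation at n = 444 it detected a true modification of 1.0 point per SD in about 13% of trials and of 1.8 points per SD in about 38%. A non-significant result is therefore weak evidence of homogeneity, and stepwise results can still be shown descriptively whatever its outcome. If the sponsor prefers to keep a post-selection test, its p-value should be calibrated, for example by permutation with the selection step repeated each time.
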